8 STATISTICAL ANALYSES

A complete description of the statistical analyses to be performed on PK as well as safety and tolerability data will be presented in a SAP.

8.1 Determination of Sample Size

CCI

Thus, assuming a CV of 40%, and under the scenario of test vs. reference ratio of geometric means of 1.0, the width of the 90% CI for the ratio of geometric means is expected to approximately be 0.25 with 52 subjects. The expected width of the 90% CI for the ratio of geometric means will slightly decrease/increase from 0.25 as the ratio of geometric means decrease/increase from 1.0.

8.2 Analysis Populations

8.2.1 Safety Population

The safety population is defined as all subjects who receive at least one dose of any study drug.

8.2.2 Pharmacokinetic Population

The PK population will include all subjects from the safety population who receive at least one dose of zavegeptan, and for whom the PK profile can be adequately characterized.

8.2.3 Pharmacokinetic Statistical Population

The PK statistical population will include all subjects from the PK population who complete at least one period of treatment for at least one PK parameter and who have not experienced any protocol deviations or other circumstances to exclude the subject from the PK statistical analysis.

A subject with pre-dose concentrations may be excluded from descriptive statistics and ANOVA if the pre-dose concentration is greater than 5% of the C_{max} value for that subject.

A subject may be excluded from the descriptive statistics and ANOVA if the subject has experienced emesis within 2 times median T_{max} for a given treatment.

8.3 Pharmacokinetic Parameters

The following PK parameters will be calculated based on the PK population by standard non-compartmental methods for zavegeptan.

- AUC_{0-t} : Area under the concentration-time curve from time zero until the last observed concentration
- AUC_{0-inf} : Area under the concentration-time curve from time zero to infinity (extrapolated)
- Residual area: Percentage of AUC_{0-inf} due to extrapolation from the time of the last observed concentration to infinity, calculated as $[1 - (AUC_{0-t}/AUC_{0-inf})] \times 100$
- C_{max} : Maximal observed concentration
- T_{max} : Time when the maximal concentration is observed
- $T_{1/2 el}$: Terminal elimination half-life
- K_{el} : Terminal elimination rate constant
- Cl/F : Apparent clearance
- V_z/F : Apparent volume of distribution

PK of Treatment C will be normalized to a dose of 100 mg.

Additional PK parameters may be calculated.

8.4 Pharmacokinetic Statistical Analysis

Statistical analysis described in this section will be based on the PK statistical population.

Individual and mean plasma concentration versus time curves will be presented for both linear and semi-log scales. Descriptive statistics (arithmetic and geometric means, standard deviation

[SD], CV%, minimum [Min], maximum [Max], and median) of the plasma concentrations versus time will be presented as well for the PK parameters.

For zavegeptan, using the MIXED procedure in SAS, with Sequence, Treatment, and Period as fixed effects, and Subject within Sequence as random effect, ANOVA will be performed on ln-transformed AUC_{0-t} , $AUC_{0-\infty}$, and C_{max} . No adjustments will be made to alpha for multiple pairwise comparisons. If the study is dosed in more than 1 Group, the statistical model may be modified to reflect the multi-Group nature. In case of a non-statistically significant Treatment by Group interaction term, the analysis will be rerun excluding this term from the ANOVA model in order to obtain ratios and confidence intervals where appropriate. The ratio of geometric means and 90% confidence intervals (A/D), (B/D), and (C/D) based on least-squares means from the ANOVA of the ln-transformed data will be calculated for $AUC_{0-\infty}$, AUC_{0-t} , and C_{max} . Other ratio of geometric means among treatments may be explored. Untransformed T_{max} will be analyzed using the MIXED model with the difference of least-squares means from the ANOVA calculated for (A-D), (B-D), and (C-D). Other differences of least-square means between treatments may be explored. The K_{el} , and $T_{1/2 el}$ will be summarized descriptively.

If the study is dosed in more than one Group the following terms will be included in the model: Group, Sequence, Sequence by Group, Period within Group, Treatment, and Treatment by Group. A random effect of Subject within Sequence by Group will also be included. If the term of Treatment by Group is found to be not statistically significant (i.e., $p > 0.05$), then the Treatment by Group term specified in the previous model would be removed from the model to calculate the ratio and 90% CI for each AUC parameter specified above and C_{max} , as applicable.

Additional PK statistical analysis may be performed.

8.5 Safety and Tolerability Analysis

Demographic parameters will be summarized descriptively. TEAEs will be summarized descriptively by treatment. Safety and tolerability analysis will be performed for all subjects in the safety population. No inferential statistical analysis of safety data is planned.

Safety and tolerability to treatments will be evaluated through the assessment of AEs (e.g., seriousness, severity, relationship to the study medication, outcome, duration, and management), vital signs, 12-lead ECG, and clinical laboratory parameters. AEs will be coded using the latest version of the MedDRA.

Any finding or absence of finding relative to each subject's baseline physical examination will be documented. Any abnormal finding noted after dosing will be documented as an AE if judged as a clinically significant change from baseline.

Changes from baseline values in vital signs, ECG, and clinical laboratory parameters will be evaluated. Clinically significant laboratory abnormalities will be identified as Grade 3 to 4 laboratory test results graded according to numeric laboratory test criteria in the latest version of CTCAE if available, otherwise according to the latest version of DAIDS Table for Grading the Severity of Adult and Pediatric Adverse Events, Corrected Version.

Additional safety and tolerability data analysis may be performed.

9 DATA COLLECTION

The electronic source data capture system is the primary data collection instrument for the study. Collection screen in the electronic source data capture system will be utilized for the collection of all data. Data will be entered using the English language and should be kept current to enable the monitor to review the subjects' status throughout the course of the study. The case report forms (CRFs) will automatically be populated using the electronic source data capture system.

Source data should be attributable, legible, contemporaneous, original, accurate, and complete. Source documents will be maintained in order to maintain data integrity. The Investigator and/or the clinical staff have the responsibility of ensuring the accuracy, completeness, legibility, and timeliness of the source data.

Details on the data management process will be described in a Data Management Plan (DMP).

10 REGULATORY CONSIDERATIONS AND QUALITY ASSURANCE

10.1 IEC/IRB Approval of Protocol and Other Study Documents

The Investigator(s) agree to provide the IEC/IRB with all appropriate documents, including a copy of the protocol/amendments, ICFs, advertising text (if any), Investigator's Brochure (if any), and any other written information provided to study subjects. The trial will not begin until the Investigators have obtained the IEC/IRB favorable written approvals for the above-mentioned study documents. A properly executed written ICF shall be read, signed, and dated by each subject prior to entering the trial or prior to performing any study procedure. The original signed and dated ICF will be kept at the clinical site and a copy will be given to the subject.

In the event that the protocol is amended, the revised protocol must be approved by the IEC/IRB prior to its implementation, unless the changes involve only logistical or administrative aspects of the trial. If a revised ICF is introduced during the study, each subject's further consent must be obtained. The new version of the ICF must be approved by the IEC/IRB, prior to subsequently obtaining each subject's consent.

The Investigator and the Sponsor's representative must sign the protocol and its amendments (if any) before initiating the study.

It is the Sponsor's responsibility to submit the protocol and its amendments (if any), and the ICFs to regulatory authorities when necessary.

10.2 Compliance

This study will be conducted in compliance with the protocol, GCP, all applicable regulations, and any IEC/IRB requirements relative to clinical studies. The study will also be conducted in compliance with the recommendations laid down in the most recent version of the Declaration of

Helsinki, with the exception that registration of such Phase 1 trials in a publicly accessible database is not mandatory. As required by the Canadian regulatory agency, a Clinical Trial Application will be submitted before the beginning of the study and a No Objection Letter must be received prior to dosing.

10.3 Quality Assurance and Monitoring

The Sponsor or its designee will perform the quality assurance (QA) and quality control (QC) activities of this study; however, responsibility for the accuracy, completeness, security, and reliability of the study data presented to the Sponsor lies with the Investigator generating the data. When applicable, QA procedures will be performed according to the site SOPs.

The study will be monitored according to the site monitoring plan and SOP to ensure that it is conducted and documented properly according to the protocol, GCP, and all applicable regulatory requirements. The Sponsor is entitled to access information about the status of the study and to review the original documents of the study.

The Sponsor may arrange audits as part of the implementation of QA to ensure that the study is being conducted in compliance with the protocol, SOPs, GCP, and all applicable regulatory requirements. In such case, audits will be independent of and separate from the routine monitoring and QC functions.

TEAE	treatment-emergent adverse event
TLFs	tables, listings, and figures
T _{max}	time when the maximal concentration is observed
ULN	upper limit of normal
V _z /F	apparent volume of distribution
WBC	white blood cells
WHO DD	World Health Organization Drug Dictionary

This document is confidential.

1 INTRODUCTION

This document outlines the pre-specified plan for the summarization and analysis of clinical data collected in Sponsor Study BHV3500-113 and is intended to give a detailed description of the summaries and the analyses that will be generated for the present study by Syneos Health or a designee. Analyses specified in this plan are based on the Biohaven Pharmaceuticals Holding Company Limited Study Protocol No. BHV3500-113, version 2.0 (Amendment 01) dated August 16, 2022 (Syneos Health Project No. 222025). Safety, tolerability, and pharmacokinetic (PK) analyses will be described.

The plan may change due to unforeseen circumstances; any changes made after the plan has been finalized will be documented. No revision to this document is required for changes which do not affect the statistical analysis methods, definitions, or rules defined in this document. If additional analyses are required to supplement the planned analyses described in this document, the changes and justification for the changes will be outlined in the associated clinical study report. No change will be made without prior approval of the Sponsor.

When applicable, all methodologies and related processes will be conducted according to Syneos Health's standard operating procedures, as appropriate. Shells for all statistical tables, listings, and figures (TLFs) referred to in this document will be displayed in a separate document.

This document is confidential.

2 STUDY OBJECTIVES

The objective of this study is to compare the rate and extent of absorption of zavegeptant 100 mg oral non-enteric coated soft gel capsule (SGC) (Test 1), zavegeptant 100 mg immediate release (IR) oral tablet + dodecylmalto side (DDM) dosage form (Test 2), zavegeptant 1 x 200 mg IR oral tablet + DDM dosage form or zavegeptant 2 x 100 mg IR tablets + DDM dosage form (Test 3), and zavegeptant (BHV-3500) 4 x 25 mg enteric coated oral SGC (Reference), under fasting conditions.

This document is confidential.

3 STUDY DESIGN

3.1 General Design

This is a Phase 1, single center, open-label, single dose, 4-period, crossover study designed to compare the PK of zavegeptan from the Test and Reference products. The study may be dosed in more than 1 Group.

The 4 sequences will be: ACBD, CDAB, BADC, and DBCA. In each period, participants will receive one of the following: Treatment A, B, C, or D on Day 1, followed by 24 hours of PK and safety assessments. On Day 2 participants will be discharged from the unit and instructed to return after at least a 7 day washout time has passed for subsequent periods of treatment.

3.2 Study Procedures

The overall schedule of procedures and assessments is provided in the protocol.

3.3 Treatment Administration

Randomization schedules will be generated through SAS® for Windows software, prior to study execution. Participants enrolled in this study will be assigned to ACBD, CDAB, BADC, or DBCA sequences using a blocked randomization.

On Day 1 of each period, participants will receive a single oral dose of one of the following oral treatments, under fasting conditions, according to the assigned sequence on the randomization schedule.

Treatment	Description
A (Test 1)	1 x 100 mg zavegeptan non-enteric coated SGC (Biohaven Pharmaceuticals Holding Company Limited) administered under fasting conditions.
B (Test 2)	1 x 100 mg zavegeptan IR tablet + DDM dosage form (Biohaven Pharmaceuticals Holding Company Limited) administered under fasting conditions.
C (Test 3)	1 x 200 mg zavegeptan IR tablet (total dose of 200 mg) + DDM dosage form. The dose for Treatment C may instead be administered as 2 x 100 mg IR tablets + DDM dosage form for a total zavegeptan dose of 200 mg (Biohaven Pharmaceuticals Holding Company Limited) administered under fasting conditions.
D (Reference)	4 x 25 mg zavegeptan enteric coated SGC (total dose of 100 mg) (Biohaven Pharmaceuticals Holding Company Limited) administered under fasting conditions.

3.4 Sample Size

Approximately fifty- two (52) healthy, non-smoking, male and female participants, aged 18 to 55 years, will be enrolled in this study.

This document is confidential.

CCI

Thus, assuming a CV of 40%, and under the scenario of test versus reference ratio of geometric means of 1.0, the width of the 90% confidence interval (CI) for the ratio of geometric means is expected to approximately be 0.25 with fifty- two (52) participants. The expected width of the 90% CI for the ratio of geometric means will slightly decrease/increase from 0.25 as the ratio of geometrics means decrease/increase from 1.0.

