3.5 Participant Withdrawal and Replacement

Over the course of the study, the Sponsor and the Investigator or designee may withdraw any participant from the study for one of the reasons described below; participant withdrawal will be done in accordance with the clinical site's SOP:

- Safety reason;
- Non-compliance with protocol requirements;
- Significant protocol deviation;
- Positive pregnancy test, drug screen, cotinine test, or alcohol breath test;
- Vomiting within 4 hours post-dose;
- Positive COVID-19 test.

Participants excluded from dosing in one period as per criteria listed above, may be invited to participate in subsequent periods of the study if deemed appropriate by the Investigator and appropriate from a statistical standpoint (i.e., would permit adequate statistical comparison). However, participants with positive pregnancy test, COVID-19 test, drug screen, cotinine test, or alcohol breath test will be definitively withdrawn from the study.

Participants experiencing emesis following study drug administration may be withdrawn. An evaluation will be done on a case-by-case basis in order to decide if withdrawal is appropriate.

Participants who withdraw, or are withdrawn, prior to dosing may be replaced. Participants who withdraw, or are withdrawn, from the study after dosing will not be replaced.

This document is confidential.

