11.4 Statistical Analyses

Statistical analysis described in this section will be based on the PK statistical population.

11.4.1 *PK Parameters in Plasma*

Individual, mean and median plasma concentration versus time curves will be presented for both linear and semi-log scales. Descriptive statistics (arithmetic and geometric means, SD, CV%, geometric mean CV%, Min, Max, and median) of the plasma concentrations versus time will be presented as well for the PK parameters.

11.4.2 *Treatment Comparisons*

For zavegepant, using the MIXED procedure in SAS, an ANOVA will be performed on ln-transformed (dose-normalized to 100 mg) AUC_{last} , AUC_{inf} , and C_{max} . No adjustments will be made to alpha for multiple pairwise comparisons. As the study was dosed in more than one Group, the following terms will be included in the statistical model: Group, Sequence, Sequence by Group, Period within Group, Treatment, and Treatment by Group. A random effect of Participant within Sequence by Group will also be included. In case of a non-statistically significant Treatment by Group interaction term, the analysis will be rerun excluding this term from the ANOVA model in order to obtain ratios and confidence intervals where appropriate. The ratio of geometric means and 90% confidence intervals (A/D), (B/D), and (C/D) based on least-squares means from the ANOVA of the ln-transformed data will be calculated for AUC_{last} , AUC_{inf} , and C_{max} . The point estimates and confidence intervals will be exponentiated using base e in order to obtain a point and interval estimate for the ratio of geometric means. Other ratio of geometric means among treatments may be explored. Untransformed T_{max} will also be analyzed using the MIXED model with the difference of least-squares means from the ANOVA calculated for (A-D), (B-D), and (C-D). Other differences of least-square means between treatments may be explored. The K_{el} , and $T_{1/2}$ will be summarized descriptively.

The SAS code to fit the model will follow the format below (using the Mixed Procedure). The input variables, datasets, and labels are depicted in italicized red text and have been given generic names.

This document is confidential.

```
proc mixed data = basepk;
  class Group Sequence Period Treatment Participant;
  model VAR = Group Sequence Sequence*Group Period(Group) Treatment
    Treatment*Group / ddfm = kenwardroger;
  random Participant (Sequence*Group);
  lsmeans Treatment;

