  estimate 'A versus D' Treatment 1 0 0 -1 / cl alpha = 0.1;
  estimate 'B versus D' Treatment 0 1 0 -1 / cl alpha = 0.1;
  estimate 'C versus D' Treatment 0 0 1 -1 / cl alpha = 0.1;
  ods output estimates = estimates tests3 = tests covparms = covparms;
run;
```

Additional PK statistical analysis may be performed.

This document is confidential.

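### Does the sample-size statement mislead by saying the 90% CI width changes only slightly as the ratio moves away from 1?

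*SAP*

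**What the plan says.** Protocol 8.1 and SAP 3.4 carry the same precision statement. With a CV of 40%, and "under the scenario of test versus reference ratio of geometric means of 1.0", the width of the 90% CI "is expected to approximately be 0.25 with fifty- two (52) participants". The protocol's version reads "is expected to approximately be 0.25 with 52 subjects". Both then describe what happens at other ratios; in the SAP, "The expected width of the 90% CI for the ratio of geometric means will slightly decrease/increase from 0.25", falling as the ratio falls and rising as it rises. No range of ratios is visible. In both documents the text just before this statement is redacted.

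Three other provisions bear on the point:

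- **Enrolment and replacement.** About 52 are to be enrolled, the same number as in the calculation. Withdrawals before dosing may be replaced (Protocol 4.4, SAP 3.5). The SAP adds: "Participants who withdraw, or are withdrawn, from the study after dosing will not be replaced".
- **Scale of analysis.** SAP 11.4.2 fits the model to ln-transformed, dose-normalized AUCs and Cmax and exponentiates the estimates and limits. The coded contrasts give 90% intervals, for example "estimate 'A versus D' Treatment 1 0 0 -1 / cl alpha = 0.1".
- **Groups.** SAP 11.4.2 begins its model description with "As the study was dosed in more than one Group". It includes a Treatment by Group term, which is dropped if it is not statistically significant.

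**The concern.** An interval that is symmetric on the ln scale becomes multiplicative after exponentiation. Its width on the ratio scale is therefore a fixed multiple of the ratio. It halves at a ratio of 0.5 and doubles at 2.0, which nobody would call slight. The reference is an enteric-coated capsule, while the tests are a non-enteric capsule and immediate-release tablets with DDM, so ratios away from 1 are conceivable.

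The 0.25 also appears to need every enrolled subject to be evaluable. Dosed drop-outs are not replaced, and SAP 11.3 removes AUCinf values when extrapolation exceeds 20% or the adjusted R-squared is below 0.9. If the Treatment by Group term stays in the model, the contrasts weight groups equally whatever their size, which can widen the interval further.

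This precision figure is the only visible statistical basis for 52 subjects. If it were wrong, the sample size would lack a sound justification and readers would misjudge how tight the results should be.

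**Working it through.** **Inputs.** CV 40%, ratio 1.0, N = 52 and the stated width of 0.25 are from SAP 3.4. The 90% level and ln scale are from SAP 11.4.2. The four-sequence, four-period design is from SAP 3.1. The visible text does not say that the CV is within-subject; that is assumed here.

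**Step 1: reproduce the 0.25.**

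- ln-scale SD: s = √ln(1 + 0.40²) = √ln(1.16) = 0.3853.
- SE of the ln ratio: s × √(2/52) = 0.3853 × 0.1961 = 0.0756.
- Degrees of freedom: 4 × 52 observations, less 52 for subjects, 3 for period and 3 for treatment = 150.
- Half-width: h = t(0.95, 150) × SE = 1.655 × 0.0756 = 0.125.
- Limits at ratio 1.0: e^(−0.125) = 0.882 and e^(0.125) = 1.133.
- Width: 0.2507.

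The figure in the plan is right. A normal quantile gives 0.249, and 50 degrees of freedom give 0.254; both also round to 0.25.

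**Step 2: other ratios.** Width = R × (e^h − e^(−h)) = 0.2507 × R.

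| Ratio R | Limits | Width | Change from R = 1 |
|---|---|---|---|
| 0.5 | 0.441, 0.567 | 0.125 | −50% |
| 0.8 | 0.706, 0.907 | 0.201 | −20% |
| 0.9 | 0.794, 1.020 | 0.226 | −10% |
| 1.0 | 0.882, 1.133 | 0.251 | 0 |
| 1.1 | 0.971, 1.247 | 0.276 | +10% |
| 1.25 | 1.103, 1.417 | 0.313 | +25% |
| 2.0 | 1.765, 2.266 | 0.501 | +100% |

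The direction matches the plan. In every row the limits are 0.882 and 1.133 times R, and the ln-scale width is 2 × 0.125 = 0.250. Relative precision does not depend on the ratio.

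**Step 3: fewer evaluable subjects, at ratio 1.0.** The visible text gives no drop-out rate; the losses below are assumed and are treated as complete.

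| Evaluable N | Width | Change from 52 |
|---|---|---|
| 51 | 0.253 | +1% |
| 47 (about 10% lost) | 0.264 | +5% |
| 42 (about 20% lost) | 0.280 | +12% |

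**Step 4: groups, if the interaction term is kept.** For two groups of n1 and n2 subjects, equal weighting multiplies the SE by √(0.25 × (1/n1 + 1/n2) × 52). The documents give no group sizes, so these are illustrations only.

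- 26/26: factor 1.00, width 0.251.
- 40/12: factor 1.19, width 0.298.
- 44/8: factor 1.39, width 0.348.

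**The case for a change.** The best argument for a change is that the sentence is false as a general description, sets no visible limit on the ratios it covers, and supports the sample size. Correcting it would cost two sentences. Redacted text might bound the range of ratios, but the visible sentence does not.

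The proportionality stands: *slightly* is accurate only close to 1. The rest does not amount to a defect.

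- **Ratios far from 1.** Neither document gives an expected ratio in its visible text. Differences in formulation make such ratios plausible but do not establish them. The doubled dose of Treatment C is not a reason, because its AUCs and Cmax are normalized to 100 mg before the comparison.
- **All 52 evaluable.** The text says approximately, and 51 evaluable still rounds to 0.25. Partial completers stay in the PK statistical population if they complete one period (Protocol 8.2.3, SAP 6.5), and some subjects left out of one period may return for later ones (Protocol 4.4, SAP 3.5). Removals under SAP 11.3 affect AUCinf and leave AUClast and Cmax untouched.
- **Allowance for losses.** The redacted text may contain one, so its absence cannot be asserted.
- **Group weighting.** Any widening depends on group sizes found nowhere in the documents and on the interaction being significant. Equal groups give none. It is a modelling matter separate from the precision statement.

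**Conclusion.** No change is needed. The stated figure is correct under its stated conditions and the direction of change is right. The only inaccuracy is one adverb, which understates a change of 20% to 25% in width at ratios of 0.8 and 1.25, and more beyond. Replacing it would gain nothing for the trial. The visible plan ties no equivalence limit, success criterion or power figure to the width, and the interval is equally informative in relative terms at every ratio. The SAP describes dosing in the past tense, so a reworded sentence there could not affect enrolment either. The reported intervals will show the precision actually achieved, including any losses.

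This rests on the CV of 40% being within-subject. The sizes for losses and groups are illustrations over assumed ranges: about 5% wider with 47 evaluable and 12% wider with 42. A reader who wants the precision at another ratio can multiply the estimate by 0.88 and 1.13.
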